7.2 Clinical Results Obtained with Combination Lenvatinib plus Everolimus Treatment

The safety and efficacy of lenvatinib and everolimus combination treatment was investigated in the randomized, multi-center, open-label trial E7080-G000-205 (Study 205) in subjects with unresectable, advanced or metastatic RCC. In the Phase 1b portion the recommended

Phase 2 dose (RP2D) for the lenvatinib/everolimus combination was determined as lenvatinib 18 mg plus everolimus 5 mg administered daily.

The Phase 2 portion enrolled subjects with advanced or metastatic, clear-cell, renal cell carcinoma who had a history of receiving one prior VEGF agent. A total of 153 subjects were randomized in a 1:1:1 ratio to receive treatment with lenvatinib (18 mg) plus everolimus (5 mg), lenvatinib (24 mg), or everolimus (10 mg) administered once daily.

The primary analysis demonstrated median PFS for lenvatinib of 7.4 months (5.6-10.2, 95% confidence interval [CI]) vs everolimus 5.5 months (3.5-7.1) vs combination 14.6 months (5.9-20.1) with a hazard ratio (HR) of combination vs everolimus of 0.40 (0.24-0.68; $p = 0.0005$) and HR of lenvatinib vs everolimus of 0.61 (0.38-0.98; $p = 0.0479$). The objective response rate (ORR) for lenvatinib was 27% (16-41), everolimus 6% (1-17%), and combination 43% (29-58%) with a median duration of objective response of lenvatinib 7.5 months (3.8-not estimable), everolimus 8.5 months (7.5-9.4), and combination 13.1 months (3.8-not estimable). The ORR ratio between combination vs everolimus was 7.2 (2.3-22.5; $p < 0.0001$) and lenvatinib vs everolimus was 4.5 (1.4-14.7; $p = 0.0067$). Updated overall survival analysis suggests a survival benefit for the combination over everolimus with an overall survival for lenvatinib of 19.1 months (13.6-26.2), everolimus 15.4 months (11.8-19.6), and the combination of 25.5 months (16.4-not estimable). The HR for combination vs everolimus is 0.51 (0.30-0.88; $p = 0.024$) and 0.68 for lenvatinib vs everolimus (0.41-1.14; $p = 0.118$) in support of a potential survival benefit with combination therapy (Motzer, et al., 2015).

The average duration of therapy for lenvatinib was 7.4 months (range 0.1-23.0), everolimus 4.1 months (0.3-20.1), and combination 7.6 months (0.7-22.6). The reported Grade 3/4 AEs included diarrhea, fatigue/asthenia, vomiting, nausea, hypertension, decreased weight and dyspnea. Discontinuations due to AEs were as follows: lenvatinib 25%, everolimus 12%, and combination 24%. The rates of AEs were generally higher for the combination arm, but they were predictable and generally managed with concomitant medication and dose modifications.

7.3 Pediatric Studies with Lenvatinib

The safety, tolerability, and activity of lenvatinib in pediatric population is being evaluated in an ongoing Phase 1/2 study E7080-G000-207 (Study 207) of lenvatinib in children and adolescents with refractory or relapsed solid malignancies. During Phase 1 portion of the study, the maximum tolerated dose (MTD) and a recommended dose of lenvatinib as a single agent in this subject population was identified. The Time-to-Event Continuous Reassessment Method (TiTE-CRM) was used to identify the recommended dose of lenvatinib (Cheung, et al., 2000). Twenty three subjects were enrolled across 3 dose groups. Three of those subjects were treated at 11 mg/m², 9 subjects were treated at 14 mg/m², and 11 subjects were treated at 17 mg/m². Twenty of 23 enrolled subjects were evaluable for dose-limiting toxicity (DLT) assessment. Three DLTs were reported at dose level 14 mg/m², including alanine aminotransferase (ALT) increase (Grade 3), hypertension (Grade 3), and hypertension (Grade 4). The Protocol Steering Committee (PSC) confirmed that the 14

mg/m² was the recommended dose for single agent lenvatinib in children and adolescents with refractory or relapsed solid tumors (Eisai Co Ltd Data on File). Phase 2 portion of Study 207 evaluating lenvatinib as a single agent or lenvatinib in combination with ifosfamide and etoposide in children and adolescents with osteosarcoma and ¹³¹I-refractory differentiated thyroid cancer is ongoing.

7.4 Study Rationale

There remains a significant unmet medical need for more effective treatment options for pediatric subjects with solid tumors. Overall solid tumors make up to 30% of all cancers in children. Approximately 80% of these tumors are cured with conventional approaches. This study will be performed on pediatric subjects with solid tumors, which were resistant to conventional therapy, and for whom there are no alternative therapies that might lead to cure.

The proposed multicenter, Phase 1/2 study (E7080-G000-216) will determine (in Phase 1 portion) a MTD and RP2D of lenvatinib administered in combination with everolimus. Phase 2 portion will estimate the antitumor activity, safety and tolerability of the lenvatinib and everolimus combination in pediatric subjects with recurrent/refractory solid tumors including HGG, rhabdomyosarcoma, and Ewing's sarcoma/pPNET.

The initial dose level (Dose Level 1) for lenvatinib will be 11 mg/m², which is approximately 80% of lenvatinib single dose MTD in pediatric subjects determined in the ongoing Study 207. The initial dose of everolimus will be 3 mg/m², which is 66% of the FDA approved dose and a dose previously found to be effective in subependymal giant cell astrocytoma (SEGA), as per everolimus package insert ([Afinitor package insert](#)).

Due to a lower starting dose determined for adult subjects with hepatocellular cancer (HCC): 12 mg (baseline body weight [BW] ≥60 kg) or 8 mg (baseline BW <60 kg) given once daily for the Phase 3 study in subjects with HCC, as opposed to the approved dose of lenvatinib monotherapy in adult subjects with differentiated thyroid cancer, which is 24 mg once daily, subjects with hepatoblastoma will be excluded from participation in this study.

8 STUDY OBJECTIVES

8.1 Primary Objectives

- **Primary Objectives for Phase 1**
 - a. To determine maximum tolerated dose (MTD) and recommended Phase 2 dose (RP2D) of lenvatinib administered in combination with everolimus, once daily to pediatric subjects with recurrent/refractory solid tumors.
 - b. To describe the toxicities of lenvatinib administered in combination with everolimus once daily to pediatric subjects with recurrent/refractory solid tumors.
- **Primary Objective for Phase 2**
 - a. To estimate the antitumor activity of lenvatinib in combination with everolimus in pediatric subjects with selected recurrent/refractory solid tumors including Ewing

sarcoma/pPNET, rhabdomyosarcoma, and HGG using objective response rate (ORR) at Week 16 as the outcome measure.

8.2 Secondary Objectives

• Secondary Objectives for Phase 1

- a. To preliminarily define the antitumor activity of lenvatinib in combination with everolimus in pediatric subjects with recurrent/refractory solid tumors.
- b. To characterize the pharmacokinetics (PK) of oral lenvatinib and everolimus, when administered in combination to pediatric subjects with recurrent/refractory solid tumors.

• Secondary Objectives for Phase 2

- a. To assess other response variables including ORR at the time of data cutoff, disease control rate (DCR), clinical benefit rate (CBR), and duration of response (DOR).
- b. To evaluate the tolerability and safety profile of lenvatinib in combination with everolimus in pediatric subjects with recurrent/refractory Ewing sarcoma/pPNET, rhabdomyosarcoma, and HGG.
- c. To characterize the PK of lenvatinib and everolimus, when administered in combination to children with recurrent/refractory Ewing sarcoma/pPNET, rhabdomyosarcoma, and HGG.

8.3 Exploratory Objectives

• Exploratory Objectives for Phase 1 and Phase 2

- a. To evaluate blood, tumor, and safety (eg, hypertension) markers as correlative biomarkers of treatment effects and outcomes of lenvatinib in combination with everolimus.
- b. To assess candidate alterations in genes and/or proteins that may contribute to tumor development and serve as predictive markers of response in archival tumor tissue from pediatric subjects.
- c. To explore relationships between lenvatinib exposure and safety (eg, AEs of special interest).

9 INVESTIGATIONAL PLAN

9.1 Overall Study Design and Plan

This is a multicenter, open-label, Phase 1/2 study of lenvatinib in combination with everolimus in pediatric subjects with relapsed or refractory solid tumors. The overall study design is depicted in [Figure 1](#).

[figure not shown]

Figure 1 Study Design

EVE = everolimus, LEN = lenvatinib, MTD = maximum tolerated dose, ORR = objective response rate, PK = pharmacokinetic, pPNET = peripheral primitive neuroectodermal tumor, RP2D = recommended Phase 2 dose.

Phase 1 Dose Escalation and Determination of the MTD

The Phase 1 component is a dose escalation study with treatment in sequential cohorts of escalating doses of lenvatinib in combination with everolimus, each administered once daily in 28-day treatment cycles. Pediatric subjects with a relapsed/refractory solid malignancy, including primary brain tumors are eligible to enroll. The initial dose level (Dose Level 1) for lenvatinib will be 11 mg/m². The initial dose of everolimus will be 3 mg/m². Dose Level 2 will escalate lenvatinib by approximately 25% to 14 mg/m² and maintain everolimus at the same dose of 3 mg/m². At Dose Levels -1 and 1, maximum daily dose of lenvatinib will not exceed 18 mg daily. At Dose Level 2, maximum daily dose of lenvatinib allowed will not exceed 24 mg. Should Dose Level 2 be well tolerated, Dose Level 3 may be considered to test lenvatinib at 14 mg/m² (capped at 24 mg) and escalate everolimus to 4.5 mg/m². For everolimus dose levels of 3 mg/m² and 4.5 mg/m², the maximum daily dose of everolimus will not exceed 5 mg and 7 mg, respectively. If the MTD for combination of lenvatinib and everolimus has been exceeded at Dose Level 1, then the subsequent cohort of subjects will be treated at Dose Level -1 with dose of lenvatinib 8 mg/m² and dose of everolimus 3 mg/m² (Table 1). Intra-subject titration of everolimus will not be allowed on this study.

At study entry, subjects must have a minimum BSA of 0.6 m².

Table 1 Planned Dose-Escalation

Dose Level	Lenvatinib mg/m ² (% Single-Agent MTD)	Everolimus (mg/m ²)
-1	8 (60% MTD) ^a	3 ^c
1*	11 (80% MTD)^a	3^c
2	14 (100% MTD) ^b	3 ^c
3 ^d	14 (100% MTD) ^b	4.5 ^e

MTD = maximum tolerated dose

*Starting dose level

a: Lenvatinib dose capped at 18 mg daily.

b: Lenvatinib dose capped at 24 mg daily.

c: Everolimus dose capped at 5 mg daily.

d: Dose Level 3 may be considered if Dose Level 2 is well tolerated.

e: Everolimus dose capped at 7 mg daily.

The Phase 1 portion of the study will utilize a rolling 6 design (Skolnik, et al., 2008). Two to 6 subjects can be concurrently enrolled into a dose level cohort.

Dose level assignment will be based on:

1. the number of subjects currently enrolled in the dose level cohort,
2. the number of DLTs observed, and
3. the number of subjects at risk for developing a DLT (ie, subjects enrolled but who are not yet assessable for toxicity).

For example, when 3 subjects are enrolled onto a dose cohort, if toxicity data is available for all 3 when the fourth subject entered and there are no DLTs, the dose will be escalated and the fourth subject will be treated at the subsequent dose level. If data is not yet available for 1 or more of the first 3 subjects and no DLT has been observed, or if one DLT has been observed, the new subject will be treated at the same dose level. Lastly, if 2 or more DLTs have been observed, the dose level will be de-escalated. This process will be repeated for Subjects 5 and 6. In place of suspending accrual after every 3 subjects, accrual will be suspended when a cohort of 6 potentially evaluable subjects has enrolled (ie, subjects enrolled but are not yet assessable for toxicity) or when the study endpoints have been met. When subjects are not evaluable for toxicity, they will be replaced with the next available subject if escalation or de-escalation rules have not been fulfilled at the time the next available subject is enrolled in the study.

The following table (Table 2) provides the decision rules for enrolling a subject at (i) the current dose level (ii) at an escalated dose level, (iii) at a de-escalated dose level, or whether the study is suspended to accrual:

Table 2 The Rolling 6 Design

# Subjects Enrolled	# Subjects with DLT	# Subjects without DLT	# Subjects with Data Pending	Decision
2	0 or 1	0, 1 or 2	0, 1 or 2	Same dose level
2	2	0	0	De-escalate*
3	0	0, 1 or 2	1, 2 or 3	Same dose level
3	1	0, 1 or 2	0, 1 or 2	Same dose level
3	0	3	0	Escalate**
3	≥2	0 or 1	0 or 1	De-escalate*
4	0	0, 1, 2 or 3	1, 2, 3 or 4	Same dose level
4	1	0, 1, 2 or 3	0, 1, 2 or 3	Same dose level
4	0	4	0	Escalate**
4	≥2	0, 1 or 2	0, 1 or 2	De-escalate*
5	0	0, 1, 2, 3 or 4	1, 2, 3, 4 or 5	Same dose level
5	1	0, 1, 2, 3 or 4	0, 1, 2, 3 or 4	Same dose level
5	0	5	0	Escalate**
5	≥2	0, 1, 2 or 3	0, 1, 2 or 3	De-escalate*
6	0	0, 1, 2, 3, or 4	2, 3, 4, 5 or 6	Suspend
6	1	0, 1, 2, 3 or 4	0, 1, 2, 3 or 4	Suspend
6	0 or 1	5 or 6	0 or 1	Escalate**
6	≥2	0, 1, 2, 3 or 4	0, 1, 2, 3 or 4	De-escalate*

DLT = dose-limiting toxicity

* If 6 subjects already entered at next lower dose level, the maximum tolerated dose (MTD) has been defined.

**If final dose level has been reached, the recommended dose has been reached.

If 2 or more of a cohort of up to 6 subjects experience DLT at a given dose level, then the MTD has been exceeded and dose escalation will be stopped. In the event that 2 DLTs observed out of 6 evaluable subjects are of different classes of Adverse Effects (eg, hepatotoxicity and myelosuppression), expansion of the cohort to 12 subjects will be considered (if one of the DLTs does not appear to be dose-related, the Adverse Effects are readily reversible, **AND** Protocol Steering Committee (PSC) **AND** sponsor all agree that expansion of the cohort is acceptable). Subjects who on PSC review are not deemed to be evaluable for DLT assessment may be replaced.

All subjects in the Phase 1 Dose Escalation phase will have samples taken for PK analysis with the intent at the end of Phase 1 of having evaluable PK data from minimally 6 subjects aged 2 to <6 years old, 6 subjects ≥ 6 to <12 years old, and 6 subjects ≥ 12 years old. Once the MTD or RP2D has been defined, 0 to 6 additional subjects will be enrolled to attain the goal of having evaluable PK data from minimally 6 subjects aged 2 to <6 years old, 6 subjects ≥ 6 to <12 years old, and 6 subjects ≥ 12 years old.

Protocol Steering Committee

The sponsor will closely evaluate the risks and benefits of the study throughout its conduct, along with the PSC as needed. The PSC may review available relevant data: DLT and safety data including laboratory assessments, 12-lead electrocardiograms (ECGs), dose administration, etc.

Toxicity Monitoring

The DLT observation period for the purposes of dose-escalation will be the first cycle of therapy. Routine Phase 1 monitoring for clinical and laboratory toxicities will be used. Blood pressure (BP) monitoring will occur at least weekly during the first 2 cycles.

Dose-Limiting Toxicity

Dose-limiting toxicity will be assessed according to Common Terminology Criteria for Adverse Events (CTCAE) v4.03 and is defined as any of the following events that are possibly, probably, or definitely attributable to lenvatinib or everolimus. Dose-limiting hematological and non-hematological toxicities are defined differently.

A. Non-hematological DLT:

- Any Grade 3 or greater non-hematological toxicity attributable to the investigational drug with the specific **exclusion** of:
 - Grade 3 nausea and vomiting <3 days duration
 - Grade 3 diarrhea <3 days duration
 - Grade 3 weight loss
 - Grade 3 liver enzyme elevation, including ALT/aspartate aminotransferase (AST)/ gamma glutamyl transferase (GGT)/ bilirubin/alkaline phosphatase that returns to Grade ≤ 1 or baseline within 7 days
 - Grade 3 asymptomatic elevation in amylase or lipase that returns to Grade ≤ 1 or baseline within 7 days
 - Grade 3 elevation in triglycerides that returns to Grade ≤ 1 or baseline within 7 days
 - Grade 3 or 4 fever <5 days duration
 - Grade 3 infection <5 days duration
 - Grade 3 hypophosphatemia, hypokalemia, hypocalcemia or hypomagnesemia responsive to oral supplementation
 - Grade 3 proteinuria (UPC) ratio >1.9 unless confirmed with a second measurement within 72 hours
 - Grade 3 headache <3 days duration responsive to optimal management.

- Any Grade 2 non-hematological toxicity that persists for ≥ 7 days and is considered sufficiently medically significant or sufficiently intolerable by subjects despite optimal supportive care that it requires treatment interruption.
- Any dose interruption or reduction due to toxicity which results in administration of less than 75% of the planned dosage of lenvatinib and/or everolimus.
- Note: Allergic reactions that necessitate discontinuation of study drug will not be considered a DLT.
- **Dose-limiting hypertension:**
 - Any Grade 4 hypertension

Confirmed systolic or diastolic BP more than 25 mmHg above 95th percentile for sex, age, height/length, or an elevated diastolic BP (ie, >95th percentile for age) not controlled by a single antihypertensive medication within 14 days of use. An antihypertensive tablet or capsule that contains up to 2 antihypertensive ingredient medications will be considered a single antihypertensive medication.

B. Hematological DLT:

- In subjects evaluable for hematological toxicity, DLT is defined as:
 - Grade 4 thrombocytopenia (platelet count $< 25,000/\text{mm}^3$) or Grade 4 neutropenia, not due to malignant infiltration.
- Any \geq Grade 2 arterial thromboembolic events (including cerebrovascular ischemia, peripheral or visceral arterial ischemia).
- Note: Grade 3 or 4 febrile neutropenia will not be considered a DLT.

All DLTs must be reported to the sponsor within 24 hours of their occurrence.

Determination of a DLT will be made by the investigator and the Eisai Medical Monitor in consultation with the PSC, as needed. Subjects who discontinue the study treatment for any reason other than DLT (eg, early disease progression) during Cycle 1 (Day 1 to Day 28), and have not received at least 75% of the prescribed dose prior to discontinuation, will be replaced.

The sponsor and PSC will review all subjects' safety and clinical data to jointly determine the MTD/RP2D of the combination of lenvatinib with everolimus. The Treatment Phase for each subject in Phase 1 ends after completing Cycle 1 of treatment unless subject discontinues early. Those subjects who discontinue study treatment in Cycle 1 transition to the Off-treatment Visit. Those who complete Cycle 1 will transition to the Extension Phase. Study treatment and tumor assessments will continue during the Extension Phase.

Phase 2 Cohorts

Once the MTD/RP2D of the combination of lenvatinib and everolimus in pediatric population has been determined in Phase 1, the Phase 2 portion of this pediatric study will commence with Cohort 1 (recurrent or refractory Ewing sarcoma/pPNET), Cohort 2 (recurrent or refractory rhabdomyosarcoma), and Cohort 3 (recurrent or refractory HGG), opening to accrual.

Cohorts 1 – 3

Phase 2 Cohorts 1 to 3 will use a 10+10 Simon's optimal 2-stage design for each cohort; 10 evaluable subjects will be enrolled to each stage. The Sponsor will closely monitor enrollment to ensure that at least 50% of subjects enrolled in each cohort are <18 years of age at the time of informed consent. The primary outcome measure for Ewing sarcoma/pPNET, rhabdomyosarcoma, and HGG will be ORR (complete or partial response) at 16 weeks. If there are no responses among the 10 subjects in Stage 1, then the enrollment to that disease cohort will stop and conclude that the lenvatinib/everolimus combination therapy does not elicit a response in that disease cohort. If there is at least 1 response in the first stage, then the second stage will enroll 10 additional evaluable subjects. If there are 2 or fewer responses among the 20 evaluable subjects, then lenvatinib/everolimus combination therapy will be declared a failure for that disease cohort. Subjects will meet the criteria for being evaluable for an objective response if they have measurable disease present at baseline and at least 1 post-baseline efficacy assessment, unless they have discontinued prior to the first efficacy assessment due to progressive disease. Subjects who are not evaluable for objective response will be replaced.

The Treatment Phase for each subject in Phase 2 ends after completing 4 cycles of treatment unless subject discontinues early. Those subjects who discontinue study treatment before completing 4 cycles transition to the Off-treatment Visit. Those who complete 4 cycles will transition to the Extension Phase. Study treatment and tumor assessments will continue during the Extension Phase.

Dosing Nomogram

The dose nomogram in [Table 3](#) provides the dose of lenvatinib to be administered for BSA increments starting from 0.6 m². BSA must be calculated on Day 1 of each cycle based on the subject's current height and body weight. The actual dose to be administered is rounded to the nearest whole number. The total lenvatinib dose is capped at 18 mg daily (Dose Levels -1 and 1), and at 24 mg (Dose Levels 2 and 3).

Table 3 Total Lenvatinib Dose (mg): Body Surface Area (m²) * Dose Level (mg/m²)

Lenvatinib Dose Levels							
8 mg/m ² Everolimus 3.0 mg/m ² Dose Level -1		11 mg/m ² Everolimus 3.0 mg/m ² Dose Level 1		14 mg/m ² (Everolimus 3.0 mg/m ²) Dose Level 2		14 mg/m ² (Everolimus 4.5 mg/m ²) Dose Level 3	
Body Surface Area (m ²)	Dose to be Administered (mg)	Body Surface Area (m ²)	Dose to be Administered (mg)	Body Surface Area (m ²)	Dose to be Administered (mg)	Body Surface Area (m ²)	Dose to be Administered (mg)
0.60 – 0.68	5	0.60 – 0.68	7	0.60 – 0.60	8	0.60 – 0.60	8
0.69 – 0.81	6	0.69 – 0.77	8	0.61 – 0.67	9	0.61 – 0.67	9
0.82 – 0.93	7	0.78 – 0.86	9	0.68 – 0.74	10	0.68 – 0.74	10
0.94 – 1.06	8	0.87 – 0.95	10	0.75 – 0.82	11	0.75 – 0.82	11
1.07 – 1.18	9	0.96 – 1.04	11	0.83 – 0.89	12	0.83 – 0.89	12
1.19 – 1.31	10	1.05 – 1.13	12	0.90 – 0.96	13	0.90 – 0.96	13
1.32 – 1.43	11	1.14 – 1.22	13	0.97 – 1.03	14	0.97 – 1.03	14
1.44 – 1.56	12	1.23 – 1.31	14	1.04 – 1.10	15	1.04 – 1.10	15
1.57 – 1.68	13	1.32 – 1.40	15	1.11 – 1.17	16	1.11 – 1.17	16
1.69 – 1.81	14	1.41 – 1.49	16	1.18 – 1.24	17	1.18 – 1.24	17
1.82 – 1.93	15	1.50 – 1.59	17	1.25 – 1.32	18	1.25 – 1.32	18
1.94 – 2.06	16	≥1.60	18	1.33 – 1.39	19	1.33 – 1.39	19
2.07 – 2.18	17			1.40 – 1.46	20	1.40 – 1.46	20
≥2.19	18			1.47 – 1.53	21	1.47 – 1.53	21
				1.54 – 1.60	22	1.54 – 1.60	22
				1.61 – 1.67	23	1.61 – 1.67	23
				≥1.68	24	≥1.68	24

The dose nomogram in [Table 4](#) provides the dose of everolimus to be administered for BSA increments starting from 0.6 m². The total everolimus dose is capped at 5 mg daily for Dose Levels -1, 1, and 2, and at 7 mg daily for Dose Level 3.

**Table 4 Total Everolimus Dose (mg): Body Surface Area (m²) *
 Dose Level (mg/m²)**

Everolimus Dose Level			
3 mg/m ² Dose Levels -1, 1, and 2		4.5 mg/m ² Dose Level 3	
Body Surface Area (m ²)	Dose to be Administered (mg)	Body Surface Area (m ²)	Dose to be Administered (mg)
0.60 – 0.83	2	0.60 – 0.77	3
0.84 – 1.16	3	0.78 – 0.99	4
1.17 – 1.49	4	1.00 – 1.22	5
≥1.50	5	1.23 – 1.44	6
		≥1.45	7

Study Duration

Approximately a total of 4.5 years from the first subject providing signed informed consent in Phase 1 to the primary endpoint completion date for Phase 2 of the study. It is estimated that the Phase 2 portion will take 3 years in order to complete the final collection of data for the primary outcome analysis.

Study duration for each subject is estimated to be:

- **Pretreatment Phase:** 4 weeks
- **Treatment Phase:** 1 cycle (4 weeks) in Phase 1; 4 cycles (16 weeks) in Phase 2.
- **Extension Phase:** Estimated maximum time of treatment is 2 years (24 cycles).
 Subjects may remain on study treatment as long as they do not meet any of the following criteria: 1) experience objective progression of disease (according to RECIST 1.1 or RANO, as appropriate), 2) exhibit no clinical benefit (in the opinion of the investigator), 3) experience unacceptable toxicity leading to withdrawal from the study, 4) withdraw or are withdrawn from the study for any reason, or, 5) termination of the study program. As long as the subject has not experienced intolerable toxicity, he or she can continue to receive study treatment. A 28-day follow up visit from last date of receiving investigational drug will be performed for subjects who discontinue study treatment.

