Third occurrence (same toxicity or new toxicity)	Interrupt lenvatinib and everolimus until resolved to Grade 0-1 or tolerable Grade 2	Reduce lenvatinib dose to 4.5 mg/m ² (or approximately 25% reduction from the previous dose level) orally once a day (1-level reduction). Dose reduction of everolimus for Grade 3 toxicity: i) if 3 mg/m ² daily everolimus at event onset, reduce to 3 mg/m ² every other day or

		ii) if 3 mg/m ² every other day everolimus at event onset, discontinue
Fourth occurrence (same toxicity or new toxicity)	Interrupt lenvatinib and everolimus	Discuss with sponsor
Grade 4^g: Discontinue Study Treatment		

Note: For grading see Common Terminology Criteria for Adverse Events (CTCAE) v4.03. Collect all CTC grades of adverse events, decreasing and increasing grade.
 
a: An interruption of study treatment for more than 28 days will require sponsor’s approval before treatment can be resumed.
 
b: Initiate optimal medical management for nausea, vomiting, hypothyroidism and/or diarrhea prior to any study treatment interruption or dose reduction.
 
c: Applicable only to Grade 2 toxicities judged by the subject and/or physician to be intolerable.
 
d: Obese subjects with weight loss do not need to return to the baseline weight or 10% of baseline weight (ie, Grade 1 weight loss). These subjects will restart the study drug(s) at a lower dose once their weight remains stable for at least 1 week and they reached the normal body mass index (BMI; if the weight loss occurred but it is still above normal BMI, they can restart the study treatment at a lower dose once the weight has been stable for at least 1 week). Normal BMI should be used as the new baseline for further dose reductions. See BMI charts for boys (Appendix 9) and girls (Appendix 10).
 
e: For Grade 2 toxicity, resume everolimus at the same dose as prior to dose interruption. For Grade 3 toxicity, investigator will decide the probability of the event being related to one or both drugs as to whether dose modification of one or both drugs is required.
 
f: For asymptomatic laboratory abnormalities, such as Grade ≥3 elevations of amylase and lipase that are not considered clinically relevant by the investigator, continuation of treatment should be discussed with the sponsor.
 
g: Excluding laboratory abnormalities judged to be non-life-threatening, in which case manage as Grade 3.
		

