9.7.1.8.1 EXTENT OF EXPOSURE

The number of cycles/days on treatment, quantity of study drug administered, and the number of subjects requiring dose reductions, treatment interruption, and treatment discontinuation due to AEs will be summarized.

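### On its literal wording the under-75% DLT rule omits permanent discontinuation, so a child stopped in Cycle 1 for an exempt drug toxicity (clearest case: Grade 4 fever under 5 days) is replaced rather than counted

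*Protocol*

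**What the plan says.** Five rules bear on the point.

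- **The under-75% rule.** Protocol 9.1 (repeated in the synopsis) makes a DLT of "Any dose interruption or reduction due to toxicity which results in administration of less than 75% of the planned dosage" of either drug. It is a separate bullet, and the list of exempt toxicities does not apply to it.
- **The exemption.** That list limits the Grade 3-or-greater non-hematological bullet. It includes "Grade 3 or 4 fever <5 days duration".
- **The mandatory stop.** For treatment-related Grade 4 toxicity, Table 5 (Protocol 9.4.1.1) gives one action: "Discontinue Study Treatment". Footnote g offers one way out: "Excluding laboratory abnormalities judged to be non-life-threatening, in which case manage as Grade 3". Fever is not a laboratory abnormality.
- **Replacement.** Protocol 9.1 says of "Subjects who discontinue the study treatment for any reason other than DLT (eg, early disease progression) during Cycle 1" that those who "have not received at least 75% of the prescribed dose prior to discontinuation, will be replaced".
- **Evaluability.** Under Protocol 9.7.1.8, a child is fully evaluable for escalation only after a DLT or after receiving at least 75% of the Cycle 1 dose.

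**The concern.** A child taken off both drugs because of drug toxicity ought to weigh against the dose level. On the literal text, one who stops early for an exempt toxicity does not: there is no DLT, too little dose was given to be evaluable, and the next child takes the place. How the event is managed then decides whether it counts. A pause long enough to bring dosing below 75% is a DLT; the permanent stop that Table 5 requires for the same Grade 4 fever is not.

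What is at stake is the escalation count. Protocol 9.1 assigns dose levels from the numbers enrolled, with DLT, and still at risk. A replaced child adds to neither the DLTs nor the evaluable total. The resulting MTD/RP2D is a primary Phase 1 endpoint and sets the Phase 2 dose.

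**Working it through.** **1. Does interruption include a permanent stop?** The protocol's usage points against it, without settling it.
- Table 5 uses interrupting and discontinuing as different instructions in different rows.
- Footnote a to Table 5 concerns interruptions after which treatment may resume, with sponsor approval beyond 28 days. It treats an interruption as temporary.
- Protocol 9.7.1.8.1 lists separately "dose reductions, treatment interruption, and treatment discontinuation due to AEs".

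**2. When does replacement apply?** Dosing is once daily for 28 days, and 75% × 28 = 21 doses.
- 20 doses: 20/28 = 71.4%, so the child is replaced.
- 21 doses: 21/28 = 75.0%, so the child is evaluable and counted as without DLT.

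**3. Effect on Table 2**, if the replacement child has no DLT.

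| Situation | Replaced | Counted as DLT |
|---|---|---|
| Cohort of 3, one such stop | 0/3: Escalate (4 treated, 1/4 = 25% stopped for toxicity) | 1/3: Same dose level |
| Cohort of 6, one such stop and one other DLT | 1/6: Escalate (7 treated, 2/7 = 28.6% affected) | 2/6: De-escalate, unless expansion to 12 is agreed |

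**4. Chance of escalating.** The plan states no figure to reproduce, so the rates here are assumptions. Let d be the rate of listed DLTs and s the rate of uncounted stops below 75% of dose. With complete data at 3 and at 6 children, escalation follows 0/3, or 1/3 then 0/3:

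P = (1 − p)³ + 3p(1 − p)²(1 − p)³

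If such children are replaced, p = d/(1 − s). If they are counted, p = d + s. The first is never larger than the second while d + s ≤ 1, so replacement can only raise the chance of escalating.

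For d = 0.20 and s = 0.02:
- Replaced: p = 0.20/0.98 = 0.204, P = 0.700.
- Counted: p = 0.22, P = 0.665.
- Difference: 3.5 percentage points.

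| d | s = 2% | s = 5% | s = 10% |
|---|---|---|---|
| 0.10 | 3.1 points | 8.4 | 17.9 |
| 0.20 | 3.5 (70.0% vs 66.5%) | 8.6 (68.6% vs 60.0%) | 16.6 (66.0% vs 49.4%) |
| 0.30 | 2.8 | 6.6 | 11.9 |

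A simulation of 400,000 cohorts at d = 0.20, s = 0.05 gave 68.6% and 59.9%, in line with the formula. If all six children are enrolled before any decision (escalate on at most 1/6), the difference at d = 0.20, s = 0.02 is 3.9 points.

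**The case against.** The strongest reply is that the bullet turns on outcome, meaning less than 75% of dose because of toxicity, and that interruption can be read to cover a stop with no restart. Two places lend support. At the fourth occurrence, Table 5 says to interrupt and consult the sponsor, with no restart assured; Protocol 9.4.1.3 does much the same for recurrent hypertension. The Note after the bullet exempts allergic reactions that force discontinuation, which may suggest that other toxicity-driven discontinuations count. That reading is open. It is not stated, and the Note already has work to do as a limit on the Grade 3-or-greater bullet.

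Discretion and reporting also soften the gap. The investigator and Medical Monitor determine DLTs, consulting the PSC as needed. The sponsor and PSC review all safety data for the MTD/RP2D. SAP 5.6.1.4 lists DLT status, including not evaluable, and SAP 5.6.2 lists AEs leading to discontinuation. The event is therefore visible, but no written rule puts the child into the Table 2 count.

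A reader might infer more than the documents support:
- **That SAP 5.6.1.3 settles the meaning of interruption.** It is a tabulation rule for exposure summaries. Under it, 11 then 0 then 8 mg/m² is not an interruption either. It does not define a DLT term.
- **That a life-threatening event is lost.** Appendix 2 gives a general guideline for Grade 4 and says that each AE has its own severity description. The one for fever is not in the documents.
- **That Grade 4 febrile neutropenia is an equally clean case.** Grade 4 neutropenia is itself a DLT in children evaluable for hematological toxicity, and the text on febrile neutropenia is unconditional: "Note: Grade 3 or 4 febrile neutropenia will not be considered a DLT". The missing word is not clearly the cause there.
- **That arterial thromboembolism shows the same gap.** Protocol 9.4.1.11 stops lenvatinib only, so a child continuing everolimus does not clearly meet the replacement rule.

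**Conclusion.** The gap is real on the literal text but narrow. It affects children permanently stopped in Cycle 1, with under 75% of dose received, for a drug-related toxicity that is otherwise exempt. Grade 4 fever under 5 days is the clear example, because the protocol itself mandates the stop. The direction is certain: compared with counting the child, replacement can only favour escalation.

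The size is not known. At an assumed 2% stop rate and 20% DLT rate, the difference is about 3 to 4 percentage points. The larger differences at 5% and 10% show sensitivity only; nothing in the documents supports those rates. Fever is not among the Grade 3/4 events named for the adult combination (Protocol 7.2) or the DLTs reported in the pediatric single-agent study (7.3).

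This rests on reading interruption as temporary, which the protocol's usage favours but does not state. It is a cheap improvement to the escalation rule, and does not show that any dose decision was wrong.

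**What to change.** In Protocol 9.1 and the synopsis, extend the opening of the under-75% bullet to cover any dose interruption, reduction or permanent discontinuation due to toxicity, and leave the rest of the bullet unchanged. Keep the allergic-reaction Note.

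For febrile neutropenia, choose one of two courses: leave it outside the change, or amend its Note to say that it is not by itself a DLT unless the under-75% criterion is met. Naming it in the bullet while the unconditional Note stands would create a contradiction.

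The protocol edit may come too late. The study was planned to begin in April 2017 with Phase 1 expected to finish within 18 months, and the SAP is dated 22 September 2022. If Phase 1 is closed, add to SAP 5.6.1.4:
- a listing of every replaced Phase 1 subject with the reason;
- the Table 2 result with drug-related Cycle 1 stops below 75% of dose counted as DLTs, allergic reactions excepted.

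The cost is one bullet in two places, or one listing with a re-tabulation. No new data are needed: doses, grades, relatedness and discontinuation reasons are already collected. The downside of the protocol edit is a slightly more conservative escalation rule.
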